3.1 Adverse Event Monitoring

All Grade 3-5 Adverse Events (AEs), regardless of being unexpected or considered to be associated with the use of the study drug will be entered into OnCore®, UCSF's Clinical Trial Management System.

Adverse Events are graded according to the Common Terminology Criteria for Adverse Events (CTCAE) as developed and revised by the Common Therapy Evaluation Program (CTEP) of the National Cancer Institute. Adverse Events are further given an assignment of attribution or relationship to treatment or medical procedure.

Attribution categories are:

- **Definite** – The adverse event is clearly related to the investigational agent(s) or medical procedure.
- **Probable** – The adverse event is likely related to the investigational agent(s) or medical procedure.
- **Possible** – The adverse event may be related to the investigational agent(s) or medical procedure.
- **Unlikely** – The adverse event is doubtfully related to the investigational agent(s) or medical procedure.
- **Unrelated** – the adverse event is clearly not related to the investigational agent(s) or medical procedure.

All Grade 3-5 adverse events entered into OnCore® will be reviewed on a monthly basis at the UCSF Site Committee meetings. All adverse events entered into OnCore® will be reviewed on a monthly basis at the UCSF Coordinating Center Site Committee meetings. All clinically significant adverse events must be reported to the UCSF Coordinating Center by the participating sites within 10 business days of becoming aware of the event or during the next scheduled monthly conference call, whichever is sooner. The UCSF Site Committee will review and discuss the selected toxicity, the toxicity grade, and the attribution of relationship of the adverse event to the administration of the study drug(s) from the UCSF Coordinating Center and the participating sites.

3.2 Serious Adverse Event Reporting

By definition, an Adverse Event is defined as a Serious Adverse Event (SAE) according to the following criteria:

- Death.
- Life-threatening (i.e. results in an immediate risk of death).
- Requires inpatient hospitalization or prolongation of existing hospitalization.
- Permanent or significant disability/incapacity.

- Gives rise to a congenital anomaly/birth defect, or cancer, or any experience that suggests a significant hazard, contraindication, side effect, or precaution that may require medical or surgical intervention to prevent one of the outcomes listed above.
- Event occurring in a gene therapy study.
- Event that changes the risk/benefit ratio of a study.
- Any other event the Principal Investigator judges to be serious or which would suggest a significant hazard, contraindication, side effect, or precaution.

Serious Adverse Event reporting will be in accordance with the UCSF IRB Regulations and Code of Federal Regulation Title 21 Part 312.32. The SAE will be reported on a Med Watch form.

UCSF IRB website for guidance in reporting serious adverse events:
<https://irb.ucsf.edu/adverse-event>

FDA website for guidance in reporting serious adverse events:
www.fda.gov/Safety/MedWatch/HowToReport/default.htm

Med Watch forms and information:
www.fda.gov/medwatch/getforms.htm

All Serious Adverse Events are entered into OnCore®, as well as submitted to the IRB (per IRB guidelines) via iRIS®. All SAEs, whether expected or unexpected, must be reported to the UCSF Coordinating Center within 1 business days of becoming aware of the event. The SAEs are reviewed and monitored by the UCSF Data and Safety Monitoring Committee on an ongoing basis and discussed at DSMC meetings, which take place every six weeks. The date the SAE was sent to all required reporting agencies will be documented in OnCore®.

If a death occurs during the treatment phase of the study or within 30 days after the last administration of the study drug(s) and is determined to be possibly, probably, or definitely related either to the investigational drug or any research related procedure, the Study Chair at the UCSF Coordinating Center or the assigned designee must be notified within 1 business day from the participating site(s) and the Study Chair must then notify the DSMC Chair or qualified alternate within 1 business day of this notification. The reporting procedure is by communication via phone or in person with written documentation of the one-on-one communication via e-mail, with a copy of the e-mail to the DSMC Manager.

Appendix 4 Translational Medicine Methods and Statistical Analysis

Compare of inflammatory genes expression by Nanostring before and after initiation of treatment on study

RNA is isolated from FFPE tumor tissue using Qiagen RecoverAll kits. RNA is run on NanoString's Human Immunology Panel v2 as described by the vendor. Analysis of the data is performed using NSolver software provided by NanoString. Samples that do not reach NanoString's Quality Control benchmarks are removed from analysis. Counts or Log2 Fold Change from screen to a post-treatment time-point are used to compare samples.

Compare relative proportion of effector versus regulatory T-cells in pre-treatment and post-treatment tumor specimens

PBMCs are thawed, washed, and rested overnight. Cells are then stained with surface markers and viability dye. After being fixed and permeabilized, any necessary intercellular staining is performed. Cells are analyzed on a BD Biosciences LDS Fortessa X-20 and resulting data is analyzed by FlowJo (TreeStar).

Compare pre-treatment to post-treatment in cytokine expression, T-cell repertoire, clonality

To assess a patient's clonality and T cell fraction, Adaptive analysis is done on DNA isolated from PBMC or FFPE tissue sample from tumor. DNA is isolated using Qiagen RecoverAll kits.

Cytokine expression is measured in patient serum using MILLIPLEX MAP High Sensitivity Human Cytokine Magnetic Bead Kit (EMD Millipore, Billerica, MA). Analysis will be performed with weighted 5 Parameter Logistic curves produced by Luminex xPONENT software. Results (pg of analyte/mL of sample) are adjusted to pg of analyte/g of tumor and averaged to produce an average expression value.

Compare pre-treatment and post-treatment populations of immune cell populations in the peripheral blood including short-lived effector cells (SLECs) and memory T-cells

PBMCs are thawed, washed, and rested overnight. Cells are then stained with surface markers and viability dye. After being fixed cells are analyzed on a BD Biosciences LDS Fortessa X-20 and resulting data is analyzed by FlowJo (TreeStar).

Compare pre-treatment to post-treatment functional immune responses using Elispot analysis

PBMCs are thawed, washed, and rested overnight before being plated in 96-well MultiScreen Filter Plates (EMD Millipore, Billerica, MA) with applicable melanoma peptides, no peptide, or a positive control peptide. Relevant cytokines secreted from activated cells are captured on the plate and visualized using Biotin/Streptavidin binding of alkaline phosphatase conjugate (ALP) with BCIP/NBT Phosphatase Substrate (MABtech, Nacka Strand, Sweden). Plates are scanned with an ELISpot reader (Cellular Technology Limited, Shaker Heights, OH) and counted using CTL Immunospot 5.0 Analyzer software. Final counts of antigen specific cytokine-secreting cells is obtained by subtracting the number of spots in the no-antigen control wells from the test wells.

Statistical Analysis

Data from all assays are graphed and analyzed for statistical significance in GraphPad Prism software. T-tests are used to determine statistical significance for comparisons between 2 groups. ANOVA tests are used to determine statistical significance for comparisons between 3 or more groups. Significance is considered reached if the p value is at or below 0.05.

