Exploratory Objectives	
• Determine whether the combination of tavo-EP, pembrolizumab, and epacadostat increases the objective response rate in SCCHN compared with emerging data for pembrolizumab in combination with epacadostat• Determine the effects of combination therapy on treated and untreated lesions by examining paired biopsy specimens for relative changes in the expression of innate and adaptive immune-specific genes, the density of CD8⁺effector versus CD4⁺regulatory TIL, evaluation of systemic inflammatory cytokines, T-cell clonality, and other hallmarks of immune activation.• Interrogate different subsets of PBMC to explore changes in phenotypic markers associated with productive systemic anti-tumor immune responses such as frequencies of short-lived effector cells and memory T cells, activated NK cells and APCs.• Explore treatment-related changes in functional immune responses using ELISpot, intracellular cytokine release and other assays.• To explore biomarkers that inform scientific understanding of this therapeutic treatment through analysis of specimens retained for future biomedical research.
------------------------	--

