Efficacy Endpoints	
Primary efficacy endpoint: Best overall response rate (BORR); defined as the percentage of patients who attain a confirmed CR or PR over the trial with the triplet treatment with a 4-week confirmatory scan per RECIST v1.1.
 
Secondary efficacy endpoints: Progression free survival (PFS) is defined as the number of days from the date of enrollment to the date of progression or death regardless of cause. Patients who do not have a documented progression or death will be censored on the date of last assessment. Overall survival (OS) is defined as the number of days from the date of enrollment to the date of death regardless of cause, patients without a death date will be censored on the date last known alive.

Exploratory / Translational Endpoints	
Translational analyses are intended to be hypothesis generating. Translational endpoints will be met if there have been significant changes in:
 
 • Inflammatory genes expression by Nanostring before and after initiation of treatment on study • The relative proportion of effector versus regulatory T-cells in pre-treatment and post-treatment tumor specimens • Pre-treatment versus post-treatment in cytokine expression, T-cell repertoire, clonality • Pre-treatment versus post-treatment populations of immune cell populations in the peripheral blood including short-lived effector cells (SLECs) and memory T-cells • Pre-treatment versus post-treatment functional immune responses using Elispot analysis • Experimental and statistical methods for these assessments are described in Appendix 4.
Safety Endpoints	
Safety assessments include AEs (either reported by the patient or observed by the Investigator), concomitant medication use, performance status, vital signs, physical examination, and laboratory assessments. AEs will be graded and reported using CTCAE version 4 and reported descriptively.

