9.3 Use in Nursing Women

It is unknown whether the study agents are excreted in human milk. Since many drugs are excreted in human milk, and because of the potential for serious adverse reactions in the nursing infant, subjects who are breast-feeding are not eligible for enrollment.

10 Correlative Studies

Tumor Biopsy:

The clinical investigator and study pathologist have the responsibility for submitting representative diagnostic material for banking. Please refer to the OncoSec Laboratory manual for detailed instructions regarding these assessments. Patients will have a research biopsy taken from at least one tumor site prior to the initiation of treatment. An additional biopsy should be taken on cycle 2 day 1(+/- 3 days) at progression/end of treatment, and additional biopsies may be performed if clinically indicated.

Biopsy Types

Punch, core, incisional, and excisional biopsy specimens are permitted and should be obtained using standard institutional practices. Tumor biopsy may be formalin fixed and paraffin-embedded or frozen at -80C. If core biopsies are used, 3-4 cores should be taken as feasible, but any attempt to acquire at least one specimen will meet protocol requirements. Fine needle aspiration biopsies are not acceptable. Biopsy requirements may be waived by the PI if biopsies pose an excess risk to the patient.

Blood Immune Response Collection:

Patients will have blood drawn for research as outlined in the *Study Calendar*. Blood for Immune response monitoring will be collected as follow: 40 ml of blood. Specimen distribution and required tubes will be specified in the laboratory manual.

Correlative Analyses:

Correlative analyses include but are not limited to:

- Analysis of paired biopsy specimens for changes in inflammatory gene expression (Nanostring), relative proportion of effector versus regulatory T cells (mIHC), evaluation of elaboration of inflammatory cytokines, T-cell repertoires, clonality, and other hallmarks of immune activation.
- Analysis of circulating T-cell populations for changes in the frequency and effector function of immune cells including short-lived effector cells and memory T cells.
- Analysis of pre- and post-treatment cytokine expression, T-cell repertoire, clonality
- Analysis of functional immune responses using Elispot and other assays.
- Additional assessments that could assist in the understanding of the immune response to cancer at the discretion of the principal investigator

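### Appendix 4's methods for the tumor T-cell ratio, ELISpot and cytokines are inconsistent with the translational endpoints, Section 10 and the enrolled population

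*Combined protocol and SAP*

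**What the plan says.** The Abstract, Section 2.4.3 and Section 7.5 all refer to Appendix 4 for the experimental methods and statistical analysis of the translational endpoints.

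**Tumor T-cell ratio.** The Abstract and Section 2.4.3 list as an endpoint "The relative proportion of effector versus regulatory T-cells in pre-treatment and post-treatment tumor specimens". Appendix 4 repeats this as a heading: "Compare relative proportion of effector versus regulatory T-cells in pre-treatment and post-treatment tumor specimens". The method beneath it starts from thawed PBMCs, stains them, and continues: "After being fixed and permeabilized, any necessary intercellular staining is performed". The separate peripheral-blood endpoint has almost the same text without that step: "After being fixed cells are analyzed on a BD Biosciences LDS Fortessa X-20". Section 10 (Correlative Studies) lists, for paired biopsy specimens, "relative proportion of effector versus regulatory T cells (mIHC"), and for biopsies it refers the reader to a "Laboratory manual for detailed instructions regarding these assessments".

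**ELISpot.** Appendix 4 plates PBMCs "with applicable melanoma peptides, no peptide, or a positive control peptide". The reported count is the spots in the test wells less those in the no-antigen wells. Section 3.3.1 requires a diagnosis of carcinoma of the head and neck.

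**Cytokines.** Appendix 4 measures cytokines in patient serum, obtains pg per mL of sample, and adjusts the result to pg per gram of tumor. The Abstract's exploratory objective reads, in part, "regulatory TIL, evaluation of systemic inflammatory cytokines, T-cell clonality". Sections 2.3 and 10 place cytokine evaluation among the measurements made on paired biopsies.

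**The concern.** Appendix 4 is where the plan says the methods are. Applied literally, it would give a blood reading for an endpoint defined in tumor, a response to peptides of a different cancer, and a serum value in a unit that needs a tumor mass.

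The T-cell ratio matters most. The Abstract's rationale attributes non-response to regulatory cells inside infiltrated lesions, and it gives the shift in the effector-to-regulatory balance as the reason for adding epacadostat. Whether the triplet achieves that shift in the tumor is the mechanistic question the biopsies are taken to answer.

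These endpoints are called hypothesis generating, but the plan also gives them a success criterion: a significant change, which Appendix 4 sets at p of 0.05 or below. A declared success should rest on an assay that measures what the endpoint names.

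**Working it through.** The documents give no effect size, sample size or power for these endpoints, so no power calculation applies. The check compares the sample, antigen and unit of each method with those of its endpoint.

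| Endpoint in Section 2.4.3 | Appendix 4 method | Fit |
|---|---|---|
| Inflammatory gene expression | NanoString on RNA from FFPE tumor | Yes |
| Effector versus regulatory T cells in tumor | Flow cytometry on PBMCs | No: wrong sample |
| Cytokines, T-cell repertoire, clonality | Serum bead assay given per gram of tumor; DNA from PBMC or tumor for clonality | Partly: cytokine unit and sample |
| Immune cell populations in blood | Flow cytometry on PBMCs | Yes |
| Functional response by ELISpot | PBMCs with melanoma peptides | No: antigen from another disease |

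Count: 2 that do not fit + 1 affected in part + 2 that fit = 5.

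**Tumor ratio.** The protocol itself treats tumor and blood as different samples. The Abstract has one exploratory objective for infiltrating cells in paired biopsies and another for PBMC subsets. Appendix 4 nevertheless gives the two endpoints nearly the same PBMC method; the one under the tumor heading adds permeabilization and further staining and mentions no tumor tissue. Section 10 gives mIHC for the ratio, but Appendix 4 contains no mIHC method. The two sections therefore conflict.

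**ELISpot.** The result is: final count = spots in test wells − spots in no-antigen wells. The second term is background, so the result depends on the peptides in the first. Only melanoma peptides are listed as test antigens. The word applicable, as written, selects among melanoma peptides and does not reach beyond them. Footnote 1 of Table 3-1 also describes prior therapy as treatment for melanoma, which suggests text carried over from another protocol. That origin is an inference.

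**Cytokine unit.** To pass from pg/mL to pg per gram of tumor one needs a volume per mass of tissue: pg/mL × mL/g = pg/g. A tissue extract has such a factor. A serum sample has no tumor mass behind it, and Appendix 4 gives no conversion. Either the word serum or the per-gram unit is wrong. The rest of the text does not say which: the Abstract calls the cytokines systemic (though inside its paired-biopsy objective), Sections 2.3 and 10 place them in biopsies, and Section 2.4.3 names no sample.

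**Reach.** Section 7.1 opens Stage 2 on at least 3 responses in 15 patients, and Section 7.3 calculates BORR from tumor response. Neither uses these assays. Section 1.3, however, says Stage 2 will be developed from the clinical and translational results of Stage 1.

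**The case against.** The best answer is that the right assay for the tumor ratio is already in the protocol. Section 10 names mIHC on paired biopsies and points to a laboratory manual, which is not available here and may hold the detail. This stands in part: the trial does plan a tumor measurement, and a reader who inferred from Appendix 4 alone that the ratio would never be measured in tumor would be going too far. But a manual does not remove a conflict between two sections of the protocol, and the endpoint text points to Appendix 4.

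A reader might also infer that all three methods fail to measure their endpoints. For cytokines the documents do not support that. A serum assay does measure systemic cytokines, which is one of the stated aims; the defect is the unit and the unsettled sample.

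Nor do the documents show that melanoma peptides were truly intended. Section 2.4.3 names no antigen, the objectives allow other functional assays, and the melanoma wording in Table 3-1 makes a drafting carry-over likely.

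Finally, it is tempting to read the t-tests in Appendix 4 as unpaired. The text does not exclude paired tests, and the log2 fold change from screening used for NanoString is already a within-patient measure. No point is made of this here.

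**Conclusion.** The inconsistency is real and should be corrected. As written, Appendix 4 disagrees with the endpoint definition and Section 10 on the sample for the tumor T-cell ratio, with the eligibility criteria on the ELISpot antigen, and with itself on the cytokine unit. Two of five translational endpoints are affected, and a third in its cytokine part.

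The size is limited to exploratory endpoints. A reader might infer that the main efficacy result or the decision to open Stage 2 is at risk. The BORR analysis and the numeric response rule do not depend on these assays. The qualification is Section 1.3: if translational results help shape Stage 2, a misdirected assay could inform that discussion.

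The conclusion rests on the text alone. What the laboratory would actually run cannot be determined from it.

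**What to change.** In Appendix 4:

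- **Tumor ratio:** specify mIHC on the paired biopsies, as Section 10 already states, and keep PBMC flow cytometry for the peripheral-blood endpoint.
- **ELISpot:** replace the melanoma peptides with antigens relevant to the enrolled disease.
- **Cytokines:** reconcile the sample across the Abstract, Sections 2.3 and 10 and Appendix 4. Report pg/mL if serum is assayed, and per gram only if tumor tissue is assayed.

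The cost is mainly wording in Appendix 4, with matching lines in the objectives where the cytokine sample is named. If the melanoma wording is carry-over, the ELISpot change is a text correction. If melanoma peptides were really planned, different reagents are needed; the documents do not say which. The text should be settled before stored samples are assayed.

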2.4.3 Exploratory and Translational Endpoints

Best overall response rate compared to emerging data for pembrolizumab in combination with epacadostat once historical comparison data for the doublet become available.

Translational analyses are intended to be hypothesis generating. Translational endpoints will be met if there have been significant changes in:

- Inflammatory genes expression by Nanostring before and after initiation of treatment on study
- The relative proportion of effector versus regulatory T-cells in pre-treatment and post-treatment tumor specimens
- Pre-treatment versus post-treatment in cytokine expression, T-cell repertoire, clonality
- Pre-treatment versus post-treatment populations of immune cell populations in the peripheral blood including short-lived effector cells (SLECs) and memory T-cells
- Pre-treatment versus post-treatment functional immune responses using Elispot analysis

The experimental methods and statistical analysis plans for these endpoints are described in Appendix 4Translational Medicine Methods and Statistical Analysis **Appendix 4**.

3 Study Design

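### Translational endpoints can be declared met on unadjusted p-values at 0.05, with no required number of changes and no statement that the tests are paired

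*Combined protocol and SAP*

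**What the plan says.** Section 2.4.3, repeated in the synopsis, makes two statements in succession. The first sets the status of the work: "Translational analyses are intended to be hypothesis generating". The second is a success rule: "Translational endpoints will be met if there have been significant changes in", followed by five families. These are inflammatory gene expression; effector against regulatory T cells in tumor; cytokines with T-cell repertoire and clonality; immune cell populations in blood; and ELISpot responses. Every family compares values before and after treatment.

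Section 7.5 defers to Appendix 4 for the analysis. There the tests are given in two sentences, "T-tests are used to determine statistical significance for comparisons between 2 groups" and "ANOVA tests are used to determine statistical significance for comparisons between 3 or more groups", and the threshold in a third, "Significance is considered reached if the p value is at or below 0.05". The paragraph covers data from all assays.

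For gene expression, Appendix 4 names the NanoString "Human Immunology Panel v2 as described by the vendor" without a gene count, and leaves the scale and the visit open: "Counts or Log2 Fold Change from screen to a post-treatment time-point are used to compare samples".

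The objectives (section 2.3) and section 10 describe the biopsies as paired. The study calendar footnotes schedule biopsies at screening, at Cycle 2 Day 1 and at progression or end of treatment, so one patient can contribute three time points.

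**The concern.** A rule that declares an endpoint met needs a known chance of doing so when nothing has changed. Three items that set that chance are missing: any adjustment for testing many analytes, the number of analytes in a family that must change, and the form of the test. On a multi-gene panel or a multiplex cytokine kit, the rule as written can be satisfied by chance hits.

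The test form matters separately. Pre- and post-treatment values from one patient are usually positively correlated. A two-sample t-test, or a one-way ANOVA across visits, would discard that information. With 15 to 28 patients per arm, the loss of power could hide real changes.

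At stake is the reading of the translational results: whether a reported endpoint that was met carries any evidential weight, and whether a negative result means much. The primary efficacy conclusion is not at stake.

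**Working it through.** The plan states no power or error rate for these analyses, so there is no figure to reproduce.

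**Inputs from the documents.** Threshold 0.05 per test (Appendix 4). Patients per arm: 15 in Stage 1 (section 7.1) and 15 + 13 = 28 over both stages (Table 4-2).

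**Assumptions, because the documents are silent.** Two-sided tests; number of tests m from 5 to 500; correlation r between analytes; correlation ρ between a patient's pre and post values; a true shift of 0.5 SD for the power figures; normal data.

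**Step 1: paired tests, independent analytes, no true change.** Each test has size 5%, so P(at least one p ≤ 0.05) = 1 − 0.95^m.

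- m = 5: 1 − 0.95^5 = 22.6%
- m = 20: 1 − 0.95^20 = 64.2%
- m = 100: 1 − 0.95^100 = 99.4%, with 100 × 0.05 = 5 false hits expected

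The chance passes 95% at 59 tests and 99% at 90.

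**Step 2: paired tests, correlated analytes.** Simulation with 28 pairs and the same correlation between all analytes (1,500 runs per cell):

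| r | m = 5 | m = 20 | m = 100 | m = 500 |
|---|---|---|---|---|
| 0.3 | 22% | 54% | 92% | about 100% |
| 0.5 | 17% | 44% | 79% | 98% |
| 0.8 | 14% | 25% | 39% | 53% |

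Correlation lowers the risk, but every cell stays well above 5%.

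**Step 3: the other reading, unpaired tests on paired data.** The mean difference has variance 2σ²(1 − ρ)/n, while the two-sample test uses 2σ²/n. For ρ > 0 its statistic is therefore too small. The paired test has noncentrality 0.5 × √n / √(2(1 − ρ)). At ρ = 0.5 this is 0.5 × √28 = 2.65 for 28 pairs and 0.5 × √15 = 1.94 for 15. Simulation (100,000 runs per setting) gives:

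| Pairs | ρ | True size, unpaired | Power, unpaired | Power, paired |
|---|---|---|---|---|
| 28 | 0.3 | 2.0% | 44% | 58% |
| 28 | 0.5 | 0.7% | 44% | 72% |
| 28 | 0.7 | 0.07% | 42% | 91% |
| 15 | 0.3 | 2.2% | 23% | 33% |
| 15 | 0.5 | 0.8% | 20% | 44% |
| 15 | 0.7 | 0.1% | 15% | 64% |

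**Step 4: whether both harms can occur together.** Put the unpaired size a into 1 − (1 − a)^m with 28 pairs. At ρ = 0.5, a = 0.00725 gives 3.6% for 5 independent tests, 13.5% for 20, 52% for 100 and 97% for 500. At ρ = 0.7, a = 0.00072 gives 7% for 100 and 30% for 500. The Step 1 figures belong to paired tests and the Step 3 power losses to unpaired tests. They coincide only when ρ is low or m is very large.

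**The case against.** The strongest reply is that the plan labels these analyses as hypothesis generating, that the primary response-rate analysis does not use them, and that the Stage 2 rule in section 7.1 depends only on at least 3 responses in 15 patients. Unadjusted p-values are common in exploratory work. This stands as a reason for lower severity. It does not remove the success rule that follows the label in the same section. Section 1.3 also says that Stage 2 will be developed from clinical and translational results, although it attaches no p-value rule to that.

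A second reply is that a paired t-test is a t-test. A reader might infer that the plan prescribes ordinary two-sample tests that ignore the pairing. The documents do not support that: Appendix 4 never says unpaired, it allows a within-patient log2 fold change, and other sections call the biopsies paired. But it also allows raw counts and speaks of groups, so what can be said is that the form is unspecified.

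A third reply is that the number of genes is not given and genes on an immune panel are likely to be correlated. This stands. A reader might infer that a false positive is almost certain. That holds for large panels with weak correlation, not for a family of five tests or a strongly correlated panel. Nor does the text say that a single hit is enough; it gives no count at all.

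Finally, 28 pairs is a favorable case. It needs Stage 2 to open and every patient to provide usable samples, whereas section 10 lets biopsies be waived and Appendix 4 drops samples that fail quality control.

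**Conclusion.** The point holds as a gap in a stated decision rule. An endpoint can be declared met on an unadjusted 0.05 threshold, across assays with many analytes, with no required number of changes and no stated test form.

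Its size depends on which reading is followed. With paired tests, the chance of at least one false hit is 23%, 64% and 99% for 5, 20 and 100 independent tests. For 100 tests it falls to about 79% at r = 0.5 and 39% at r = 0.8. With unpaired tests, at ρ = 0.5 and a 0.5 SD shift, power is about 44% instead of 72% with 28 pairs, and 20% instead of 44% with 15. Panel size, correlations and shift are all assumptions.

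A reader might add the two together and conclude that the plan both inflates false positives to near certainty and loses power. The documents and the arithmetic do not support that: the unpaired test loses power because it is conservative, which also lowers its false-positive rate. Severity is low to moderate.

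**What to change.** In Appendix 4:

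- Specify paired t-tests or Wilcoxon signed-rank tests on within-patient change, using log2 fold change for gene expression, and name the primary post-treatment visit.
- For three or more time points, specify a mixed model with a patient effect.
- Within each multi-analyte assay, control the false discovery rate at a level fixed in advance. The level is the team's choice. With independent tests and no true change anywhere, Benjamini-Hochberg keeps the chance of any hit in that assay at or below the chosen level, against 99% for 100 unadjusted tests.
- Define when an endpoint is met, either on the adjusted result (stating how many analytes must pass) or on one prespecified summary measure per family. Otherwise delete the success rule from section 2.4.3 and the synopsis and report the results as descriptive.

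The cost is a few lines of text and fewer nominal hits to report. It needs no extra patients, samples or assays.
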